6 STUDY PLAN AND PROCEDURES

6.1 Study Schedule

From study entry, patients will be assessed every 21 days, prior to the administration of each dose of pembrolizumab. During week 3 of SBRT for MPM, patients will have an additional clinical review. Patients will continue to be assessed and stay on pembrolizumab until they have disease progression, suffer unacceptable toxicities, withdraw, the study ends or have completed 35 cycles of pembrolizumab. Treatment beyond progression or 35 cycles needs to be discussed with the study sponsor and MSD. Patients will be required to attend a safety visit 30 days after their last dose of pembrolizumab.

If the patient has not progressed at the last dose of pembrolizumab they will be reviewed every 9 weeks until the start of new anti-cancer therapy, disease progression, death, withdrawal or end of the study. Patients that have progressed or begin a new anti-cancer treatment will enter into the survival follow up phase and an update will be sought every 12 weeks to assess for disease status until death, withdrawal of consent, or the end of the study, whichever occurs first. Survival follow up can be done over the phone.

The schedule of assessments to be performed at each visit is summarised in Table 3. Individual trial procedures are described in detail below. It may be necessary to perform these procedures at unscheduled time points if deemed clinically necessary by the Investigator. Furthermore, additional evaluations/testing may be clinically indicated for reasons related to patient safety. In some cases, such evaluation/testing may be potentially sensitive in nature (e.g., HIV, Hepatitis B, Hepatitis C, etc.) and will be performed in accordance with local regulations.

Table 3: Study Schedule of Assessments

Trial Phase:	Screening period	Initial phase			Maintenance phase DLT period (Pembrolizumab 200 mg q3wkly)			Maintenance phase ⁽¹⁰⁾ Beyond DLT period (Pembrolizumab 200 mg q3wkly)			End of Treatment (If applicable)	Post-Treatment				
		Radiotherapy phase (30 Gy 3#)			C2, D1	C3, D1	C4, D1	C5, D1	C6, D1	C7, D1	C8, D1	C X ¹⁰ , D1	Discontinuation of Pembrolizumab	Safety Follow- up (SFU)	Follow Up	Survival Follow Up
		C1, D1	C1, D15	C1, D17										30 days after last dose	Every 9 weeks from SFU	Every 12 weeks from SFU
Treatment Cycle/Title:					±3	±3	±3	±3	±3	±3	±3	±3	±3	±7	±7	±7
Scheduling (Day):	-28 to -1															
Informed Consent	X															
Inclusion/Exclusion	X															
Clinical history	X															
Full Physical Exam	X	X												X	X	
Directed Phys. Exam			X	X	X	X	X	X	X	X	X	X	X			
Adverse Events	X	X	X	X	X	X	X	X	X	X	X	X	X	X	X	
MRC dyspnoea score	X		X	X	X	X	X	X						X		
Medications	X	X	X	X	X	X	X	X	X	X	X	X	X	X	X	
ECOG PS	X	X	X	X	X	X	X	X	X	X	X	X	X	X	X	
Vital Signs ⁹ & Weight	X	X		X		X	X	X	X	X	X	X	X	X	X	
Height	X															
Haem & Biochem	X ⁶	X ⁷			X ⁷	X ⁷	X ⁷	X ⁷	X ⁷	X ⁷	X ⁷	X ⁷	X	X		
fT ₃ , fT ₄ and TSH	X ⁶	X				X		X		X		X	X	X	X	X
PT and aPTT	X ⁶															
Pregnancy Test	X ⁸				X ⁸	X ⁸	X ⁸	X ⁸	X ⁸	X ⁸	X ⁸	X ⁸		X ⁸		
Urinalysis	X ⁶															
Pembrolizumab		X			X	X	X	X	X	X	X	X	X			
Radiotherapy			X ⁵	X ⁵	X ⁵											
Pulmonary function ³	X															
Imaging	CT ¹ & CXR ²			CXR	HRCT	CXR	CT	CXR		CT		X ¹	CT		CT	
PD-L1 assessment ⁴	X															
OPTIONAL Research Blood ⁷		X			X			X					X			
Survival Status																X

1. Imaging with a CT scan should occur during the screening period as a baseline and then every 9 weeks (3 cycles) for the first 6 months, then every 12 weeks after 6 months (regardless of treatment delays). Imaging with CT scanning can occur 7 days before the visit to ensure that the results are available at the visit.
2. Chest x-ray will be performed during the dose limiting toxicity period in order to monitor for pneumonitis. A High-Resolution CT chest should be performed prior to commencing C2D1.
3. Full pulmonary function tests should be performed at baseline.
4. PD-L1 testing will be batched and performed once all patients are on study.
5. SBRT for MPM will be administered on C1D15, C1D17 and C1D19.
6. Screening laboratory investigations will be performed within 10 days prior to C1D1.
7. Safety laboratory investigations will be performed no more than 72 hours prior to D1 dosing with Pembrolizumab.
8. Serum pregnancy test should be performed at baseline for females of childbearing potential within 72 hours of D1C1 Pembrolizumab. Additional urine pregnancy test would be performed at each cycle of Pembrolizumab during the treatment period and at the Safety Follow-up visit.
9. Vital signs include temperature, pulse, respiratory rate, oxygen saturation and blood pressure.
- 10.

Maintenance pembrolizumab will continue until disease progression, withdrawal of consent, or unacceptable toxicity. The assessments at CXD1 will be repeated on D1 of each additional cycle until the end of patient maintenance phase participation and also if the patient restarts treatment on disease progression. Patients obtaining complete response or having completed 35 cycles of pembrolizumab must discontinue and may

recommence for additional 17 cycles upon subsequent disease progression. In patients who restart treatment on disease progression, once the treatment period is completed, they will also attend the Safety Follow-up Visit as detailed in the protocol.

6.2 Administrative Procedures/Assessments

6.2.1 Informed Consent

It is the responsibility of the Investigator / designee to give each patient, prior to inclusion in the trial, full and adequate verbal and written information regarding the objective and procedures of the trial and the possible risks involved. Sufficient time should be allowed for the patient to decide on trial entry. Patients must be informed about their right to withdraw from the trial at any time. Written patient information must be given to each patient before enrolment. The written patient information is an approved patient information sheet (PIS) according to national guidelines.

The Investigator must obtain documented written informed consent from each potential patient prior to participating in a clinical trial. Consent must be documented by the patient's dated signature on a consent form along with the dated signature of the person conducting the consent discussion. If the patient is illiterate, an impartial witness should be present during the entire informed consent reading and discussion. Afterwards, the patient should sign and date the informed consent, if capable. The impartial witness should also sign and date the informed consent along with the individual who read and discussed the informed consent. Only the Chief Investigator (CI), Co-Investigators and those Sub-Investigator(s) delegated responsibility by the CI, having signed the delegation of responsibilities log, are permitted to gain informed consent from patients and sign the consent form. All signatures must be obtained before the occurrence of any medical intervention required by the protocol.

A copy of the signed and dated consent form should be given to the patient before participation in the trial. The original consent form should be stored in the site file with a copy also being placed in the patient's medical notes. Results from tests conducted as part of patients' standard care may be used as part of screening to determine eligibility as long as the tests were conducted within the acceptable time window.

The initial informed consent form, any subsequent revised written informed consent form and any written information provided to the patient must receive the REC approval/favourable opinion in advance of use. The patient should be informed in a timely manner if new information becomes available that may be relevant to the patient's willingness to continue participation in the trial. The communication of this information will be provided and documented via a revised consent form or addendum to the original consent form that captures the patient's dated signature. The informed consent will adhere to REC requirements, applicable laws and regulations.

6.2.2 Inclusion/Exclusion Criteria

All inclusion and exclusion criteria will be reviewed by the Investigator or qualified designee to ensure that the patient qualifies for the trial.

6.2.3 Demographic Data, Medical History and Treatment History

Demographic data collected will include date of birth and race/ethnicity. A medical history will be obtained by the Investigator or qualified designee. Medical history will include all active conditions, and any condition diagnosed within the prior 10 years that are considered to be clinically significant by the Investigator. Details regarding the disease for which the patient has enrolled in this study will be recorded separately and not listed as medical history. In addition to the medical history the Investigator or qualified designee will obtain details the patient's current disease status and treatment history including prior and current details regarding disease status, in addition to all prior cancer treatments including systemic treatments, radiation and surgeries.

6.2.4 Subsequent Anti-Cancer Therapy Status

Patients that discontinue from pembrolizumab for any other reason than disease progression will have a follow-up visit every 9 weeks in which the Investigator should review all new anti-cancer therapy initiated after the last dose of pembrolizumab. If a patient initiates a new anti-cancer therapy within 30 days after the last dose of trial treatment, the 30 day Safety Follow-up visit must occur before the first dose of the new therapy. Once new anti-cancer therapy has been initiated the patient will move into survival follow-up.

6.2.5 Survival Status

The Investigator or qualified designee will assess the patient for survival status. The assessment will include the patient status and if applicable details of patient death or detail if patient has been lost to follow-up. Survival follow up can be done over the phone.

6.2.6 Prior and Concomitant Medications Review

6.2.6.1 Prior Medications

The Investigator or qualified designee will review prior medication use, including any protocol-specified washout requirement, and record prior medication taken by the patient within 28 days before starting the trial. Treatment for the disease for which the patient has enrolled in this study will be recorded separately and not listed as a prior medication.

6.2.6.2 Concomitant Medications

In addition the investigator or qualified designee will record all medication, if any, taken by the patient during the trial. All medications related to reportable SAEs and overdose and liver toxicity events of clinical interest (ECIs) should be recorded as defined in Section 8.

6.3 Clinical Procedures/Assessments

6.3.1 PD-L1 Assessment

To participate in the trial patients need available tissue of a tumour lesion not previously irradiated (tumours progressing in a prior site of radiation are allowed) for PD-L1 characterisation. This specimen will be evaluated at a central laboratory for expression status of PD-L1 by the PD-L1 IHC 22C3 pharmDx (Dako). If no tissue is available, then following informed consent they should undergo a biopsy of a tumour lesion for biomarker analysis. NOTE: Patients participating in this trial will be unselected for their PD-L1 status.

6.3.2 Adverse Event (AE) Monitoring

The Investigator or qualified designee will assess each patient for potential new or worsening AEs as specified in the schedule of study assessments (Table 3) and more frequently if clinically indicated. AEs will be graded and recorded from confirmation of entry into the trial until the patients 30 day safety follow up visit according to CTCAE v5.0 (see Appendix 4). Toxicities will be characterised in terms regarding seriousness, causality, toxicity grading, and action taken with regard to trial treatment.

All AEs of unknown aetiology associated with pembrolizumab exposure should be evaluated to determine if it is possibly an event of clinical interest (ECI) or a potentially an immune related adverse event (irAE). See Appendix 5 regarding the identification, evaluation and management of AEs of a potential immunological aetiology. Please refer to section 8 for detailed information regarding the assessment and recording of AEs.

6.3.3 MRC dyspnoea Score

The Investigator or qualified designee will assess the patient's dyspnoea using the MRC Dyspnoea Score (Appendix 2) at screening period and the time points defined in the study schedule of assessments (Table 3).

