In the initial safety cohort, a minimum of 3 patients will be treated at the SBRT dose of 30Gy in 3 fractions combined with pembrolizumab. The gap left between the treatments of each subsequent patient will start after the second cycle of Pembrolizumab in the previous dosed patient to mitigate against multiple patients suffering from acute toxicity. The DLT period for this study is 12 weeks from the last dose of SBRT (i.e. at C6D1). Patients included in Part A will be considered by the Safety Review Committee (SRC) once the 3rd and 6th patient in the Part A cohort has completed the DLT period. If 0 out of 3 patients experience a DLT, or if 1 out of 3 patients experience a DLT in Part A, then the cohort will be expanded to 6 patients. If 1 in 6 patients experience a DLT, then it will be acceptable to move forward to the expansion cohort (Part B). However, if ≥ 2 in 6 patients (or more than 1 in the first 3 patients) experience a DLT then the maximum administered dose

(MAD) will have been reached. If the MAD is seen at a dose level of 30 Gy in 3# then the study will be terminated.

While waiting for 3 or 6 patients to complete the DLT period, no additional patients will be recruited. Further patients can only be recruited after the SRC has reviewed the toxicity data for the cohort to proceed to Part B. Patients obtaining complete response or having completed 35 cycles of pembrolizumab must discontinue and may recommence for additional 17 cycles upon subsequent disease, the CI/PI will need to discuss with the sponsor and MSD, on a case by case basis for the continuation of pembrolizumab.

Table 1: SBRT dose level and pembrolizumab dosing during the initial safety cohort and expansion phase.

Dose Level	Pembrolizumab Dose	SBRT to part of a MPM lesion
Initial safety cohort	200 mg i.v. over 30 minutes, every 3 weeks	30 Gy in 3# (Monday, Wednesday, Friday)
Expansion cohort	200 mg i.v. over 30 minutes, every 3 weeks	30 Gy in 3# (Monday, Wednesday, Friday)

SBRT: Stereotactic Ablative Body Radiotherapy; Gy: Gray; i.v.: intravenous; mg: milligrams; #: fraction.

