4.2.1 Dose Limiting Toxicities

Acute toxicity will be assessed up to and including 3 months following the final fraction of radiotherapy (i.e. at C6D1). The MRC dyspnoea score (Appendix 2) will be used to assess dyspnoea at baseline/on treatment and the Common Toxicity Criteria for Adverse Events (CTCAE) version 5.0 will be used to grade all drug and SBRT observed toxicities (Appendix 4). The SRC will consider expansion after the 6th patient in the initial safety cohort has completed the DLT period and reviewed the toxicities before recruitment to the expansion cohort Part B.

Any DLT must be a toxicity that is considered probably, possibly or definitely related to the combination of pembrolizumab and SBRT. DLT is defined as follows:

Haematologic:

- Neutropenia with fever grade 3 or neutropenia grade 4
- Thrombocytopenia with bleeding grade 3 or thrombocytopenia grade 4

Non-Haematologic:

Any ≥ 3 non-haematological toxicity which is definitely, probably or possibly related to the combination of pembrolizumab and SBRT for pleural mesothelioma including the following:

- Increased MRC dyspnoea score > 2 grades from baseline and/or acute dyspnoea grade ≥ 4 (or CTCAE dyspnoea grade ≥ 3) persisting for > 7 days (including weekend).
- Pneumonitis grade ≥ 3 persisting for > 7 days (including weekend).
- Oesophagitis grade ≥ 3 persisting for > 7 days (including weekend).
- Toxicity leading to interruption of radiotherapy for > 7 days (including weekend).

Progression of the study will not proceed until the following criteria are satisfied by the SRC:

- If 0 out of 3 patients experience a DLT, or if 1 out of 3 patients experience a DLT, a further 3 patients will be recruited at the dose level in the initial safety cohort.
 - If 0 out of 6 patients experience a DLT, or if 1 out of 6 patients experience a DLT, then progression to Part B of the study can proceed.
 - If ≥ 2 out of 6 patients (or more than 1 in the first 3 patients) experience a DLT, then there will be no Part B expansion phase and the study will be terminated.

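### Table 3 schedules no MRC dyspnoea score at C6D1, the visit that closes the DLT window, although an MRC rise is part of the DLT definition

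*Protocol*

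**What the plan says.** All references are to the protocol.

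- **Window.** Section 4.2: "The DLT period for this study is 12 weeks from the last dose of SBRT (i.e. at C6D1"). Section 4.2.1 uses the same closing visit: "Acute toxicity will be assessed up to and including 3 months following the final fraction of radiotherapy (i.e. at C6D1").
- **Criterion.** The first bullet of the non-haematological DLT list in section 4.2.1 begins "Increased MRC dyspnoea score > 2 grades from baseline". It is joined by an and/or to dyspnoea grade criteria and carries a persistence requirement of more than 7 days.
- **Intended use.** Section 4.2.1 says the MRC score "will be used to assess dyspnoea at baseline/on treatment". It gives no point at which scoring stops.
- **Timing.** Section 6.3.3 leaves this to the schedule: "MRC Dyspnoea Score (Appendix 2) at screening period and the time points defined in the study schedule of assessments (Table 3").
- **Schedule.** In Table 3 (section 6.1), the row labelled "MRC dyspnoea score" has eight marks: one at screening, a blank, six in succession, five blanks, then one in an end-of-treatment or safety-visit column. The adverse-event and ECOG rows are marked without a break from screening past C6D1.

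**The concern.** The text runs the DLT window to C6D1 and makes a change in MRC score one way of meeting the DLT definition. The table that governs when the score is taken stops before that visit. A patient whose MRC score worsens after the last marked visit has no scheduled score to show it, so the Safety Review Committee could count that patient as free of a DLT on this criterion.

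The DLT proportion in Part A is the primary analysis (section 9.1.1). A missed event can only lower it. Under section 4.2.1, 1 DLT in 6 patients opens Part B and 2 in 6 terminates the study, so one patient can reverse the decision.

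**Working it through.** **Inputs.** Cycle length is 21 days (section 6.1). Fractions are fixed by a Table 3 footnote: "SBRT for MPM will be administered on C1D15, C1D17 and C1D19". The window is 12 weeks, or 84 days (section 4.2).

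**Step 1: reproduce the plan's own equivalence.** Day 1 of cycle n falls on study day 1 + 21(n − 1).

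- C4D1 = 1 + 63 = day 64; C5D1 = 1 + 84 = day 85; C6D1 = 1 + 105 = day 106.
- The last fraction is day 19, so the 84 days end on day 19 + 84 = day 103.
- C6D1 is 106 − 19 = 87 days after the last fraction. That agrees with 84 days within the ±3-day visit window, so the protocol's pairing of 12 weeks with C6D1 is sound.

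**Step 2: locate the MRC marks.** In the available copy the MRC row has 16 cells, with marks in cells 1, 3 to 8 and 14. The header has also lost its structure and shows no C1D19 column, so two alignments are possible.

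| | 16 columns (no C1D19) | 17 columns (C1D19 included) |
|---|---|---|
| Cells 3 to 8 | C1D15, C1D17, C2D1, C3D1, C4D1, C5D1 | C1D15, C1D17, C1D19, C2D1, C3D1, C4D1 |
| Cell 14 | Safety follow-up | Discontinuation |
| C5D1 | Marked | Blank |
| C6D1 | Blank (cell 9) | Blank (cell 10) |

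If there are 17 columns and the 16-cell row has lost one blank, the result for C6D1 does not change. Wherever that blank sat, the sixth successive mark falls on C4D1 or C5D1, never on C6D1.

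**Step 3: which alignment?** The other rows disagree.

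- *For 16 columns:* research blood falls at C1D1, C2D1, C5D1 and discontinuation, matching section 6.3.13. High-resolution CT falls at C2D1, CT at C4D1 and C7D1, and the haematology and pregnancy marks fall on dosing visits.
- *For 17 columns:* the three radiotherapy marks need three columns. Vital signs then cover every dosing visit, and adverse-event marks end at the safety visit.
- *Neither:* the pembrolizumab row has nine marks after C1D1, but only eight columns (C2 to C8 and CX) can hold them.

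C5D1 therefore cannot be settled from this copy.

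**Step 4: size of the gap.**

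| Last in-window score | Days after last fraction | Days of window left | Share of 84 |
|---|---|---|---|
| C5D1 (day 85) | 85 − 19 = 66 | 103 − 85 = 18 | 21% |
| C4D1 (day 64) | 64 − 19 = 45 | 103 − 64 = 39 | 46% |

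**Step 5: who could be missed?** Entry requires an MRC score below 3 (section 5.4.1). A rise of more than 2 grades therefore means 0 to 3 or worse, 1 to 4 or worse, or 2 to 5. MRC 4 is breathlessness on undressing (Appendix 2), and the general CTCAE guide in Appendix 4 places limits on self-care, dressing included, at grade 3. Rises to 4 or 5 would therefore most likely also be graded 3 or more as adverse events. A rise from 0 to 3, meaning breathlessness within 100 yards, need not be.

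**The case against.** The strongest reply is that little depends on the blank cell.

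- Adverse events are assessed at both C5D1 and C6D1 on either alignment, and any related non-haematological toxicity of grade 3 or more is already a DLT. This stands, and it confines the exposure to the MRC-only route.
- The MRC bullet sits under a heading about grade 3 or higher toxicity, so it might be read as adding nothing of its own. The and/or wording points the other way, but the text is not explicit.
- The criterion needs persistence beyond 7 days, which three-weekly scores cannot establish alone. Section 6.1 allows unscheduled assessments, and section 7.1.2 says a dyspnoea score will be recorded without naming a cut-off. Both are true, but neither requires a score at the closing visit.
- The table is damaged, and damage is not an error in the plan. That rules out a firm statement about C5D1. It does not rescue C6D1, which is blank on both alignments.

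A reader might infer more: that scoring stops about halfway through the window, that C5D1 is certainly unscored, and that 46% is the established gap. All three depend on the 17-column alignment, which the research-blood, imaging and laboratory rows contradict. A reader might also fault the blank at C1D1. Table 3 uses screening as the baseline for CT and lung function, and MRC is scored at screening, so a fresh score at C1D1 is a preference and not a correction.

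**Conclusion.** The point holds in a limited form. Table 3 has no MRC score at the visit that closes the DLT window, and this does not fit section 4.2.1. The share of the window after the last scheduled score is 21% if C5D1 is marked and 46% if it is not; the original table must decide.

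The effect is one-directional: it can only reduce the Part A DLT count. It needs a patient with a late, related, persistent MRC rise (mainly 0 to 3), not graded 3 or more under CTCAE, and not scored at an unscheduled assessment. That is a narrow case, but one such patient is enough to turn 2 of 6 into 1 of 6.

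The conclusion assumes that visits run on schedule, that the MRC rise is a separate route to a DLT, and that the copy of the MRC row is right to within one lost blank. The documents do not support saying that late dyspnoea goes unmonitored or that the primary endpoint cannot be assessed. The point is worth correcting but does not undermine the design.

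**What to change.** Reconcile Table 3 with section 4.2.1 by marking the MRC score at every Day 1 visit through C6D1. That means adding C6D1, and adding C5D1 if the original table shows it blank. Scheduled scoring would then run to the end of the window on either alignment.

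The cost is an edit to the schedule and the CRF. It is a one-line score at visits where adverse events and ECOG status are already taken. Sample size, decision rule and analysis are unchanged.
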